### **2.1.6 Secondary Outcomes**

#### **2.1.6.1 Frequency of Cardiopulmonary Events**

The number of cardiac events will be measured as the occurrence of any cardiac and cardiac-related events, not limited to:

1. In-hospital Death

2. In-hospital Cardiac Arrest

3. Composite cardiovascular outcome or intervention (Lethal Arrhythmias , Acute Pulmonary Edema, Cardiogenic Shock, Myocardial Infarction, Percutaneous Coronary Intervention, Coronary artery Bypass Surgery , New or Recurrent MI, Recurrent Ischemia requiring Revascularization)

\*all within 72 hours of presentation to the ED

#### **2.1.6.2 Cardiac Arrest**

Cardiac arrest will be defined as the event of developing ventricular fibrillation, having a sudden unexpected death, or having a resuscitation event requiring cardiopulmonary assistance (chest compressions and/or defibrillation).

## **2.2 Subject Screening and Eligibility Criteria**

### **2.2.1 Subject Recruitment and Screening**

Subjects aged 18 years or older who meet the following inclusion and exclusion criteria.

## 2.2.2 Inclusion Criteria

Candidates for this study must meet all of the following Inclusion criteria:

1. 18 years of age or older;
2. Admission to emergency department requiring immediate medical attention which is presumed to be cardiac or cardiopulmonary related and considered 2nd or 3rd tier priority in triage system. Symptoms including:
  - Shortness of breath
  - Skin pallor consistent with cardiopulmonary complications
  - Chest pain
  - Rapid or irregular heartbeat

And any symptoms considered to be cardiac or cardiopulmonary-related by the investigator

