A novel algorithm for determining risk of acute cardiac complications, including cardiac arrest, for patients presenting to the ED has recently been reported. Unlike prior risk stratification tools that relied on basic vital sign data, this algorithm utilizes multiple metrics of heart rate variability (HRV) as well as a machine learning approach to solve the risk classification problem. The algorithm requires the collection of vital sign data, patient mental status, and *at least* 5 minutes of continuous electrocardiography (to calculate HRV metrics). It was shown to be more accurate than MEWS in predicting cardiac arrest within 72 hours of admission to hospital. Furthermore, the algorithm has been used to predict serious complications (mortality, cardiac arrest, ventricular tachycardia, hypotension requiring inotropes or intra-aortic balloon pump (IABP) insertion, intubation or mechanical ventilation, complete heart block, bradycardia requiring pacing, and recurrent ischemia requiring revascularization) within 72 hours in patients presenting to the ED with chest pain. In this patient population, a score of 4 or higher from the algorithm had a sensitivity of 0.880, specificity of 0.680, positive predictive value of 0.195, and a negative predictive value of 0.985 which was better than using ST elevation/depression and troponin in predicting complications within 72 hours. The primary limitation of the algorithm is that it has been developed and tested in Singaporean patients. Verification of the results of the studies using this algorithm in other patient cohorts is required. As such, the proposed study will investigate the sensitivity and specificity of the algorithm.

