### 2.3.2 Evaluation Requirements

#### 2.3.2.1 Assessments

The following data points will be recorded:

- Inclusion/Exclusion Criteria
- Demographics (date of birth/age, gender and ethnicity)
- Smoking status
- ED diagnosis (primary)
- Final diagnosis (primary)
- Medications including beta-blockers, combined alpha and beta-blockers, digitalis, calcium channel blocker, bronchodilators, amiodarone, other anti-arrhythmics

- Medical history, specifically a history of ischemic heart disease, diabetes, hypertension, dyslipidemia, stroke, cancer, respiratory disease, renal disease, congestive heart disease, PCI, CABG, MI)
- Physical exam [REDACTED]  
[REDACTED]  
[REDACTED]
- 12-lead ECG (if patient is reporting chest pain)
- Continuous 3-lead ECG recording of *at least* five minutes within 30 minutes of ED triage
- Chest Pain
- Symptom onset/peak within 24 hours of presentation
- Pain score
- MEWS Score
- Cardiopulmonary events (acute pulmonary edema, lethal arrhythmias, cardiogenic shock, myocardial infarction, percutaneous coronary intervention, coronary artery bypass surgery, recurrent ischemia requiring revascularization)
- In-hospital cardiac arrest
- In-hospital death
- Status changes (admitted to ICU, admitted to ward, etc.)
- Length of stay

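### The only accuracy figures quoted come from ED chest-pain patients, but a broader symptom mix is enrolled and analysed as one group by a model AUC, so cohort and case-mix effects cannot be separated and the published cut-off is never evaluated

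*Combined protocol and SAP*

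**What the plan says.** **Source of the figures.** Section 1.1 reports that "a score of 4 or higher from the algorithm had a sensitivity of 0.880", with "specificity of 0.680, positive predictive value of 0.195, and a negative predictive value of 0.985". It attributes these to a study of serious complications "within 72 hours in patients presenting to the ED with chest pain". The same section cites a second result, that the algorithm was "more accurate than MEWS in predicting cardiac arrest within 72 hours of admission to hospital". That result carries no accuracy figure and is not described as limited to chest pain.

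**Reason for the study.** The stated limitation is that development and testing took place in Singaporean patients: "Verification of the results of the studies using this algorithm in other patient cohorts is required". Section 1.1 ends by saying that "the proposed study will investigate the sensitivity and specificity of the algorithm".

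**Who is enrolled.** Section 2.2.2 admits adults in the second or third triage tier with a presumed cardiac or cardiopulmonary cause. The listed symptoms are breathlessness, pallor, chest pain and palpitations, followed by: "And any symptoms considered to be cardiac or cardiopulmonary-related by the investigator".

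**What is analysed.** Section 3.2 plans one binary logistic model with unnamed explanatory variables, an ROC curve and its AUC. Section 3 names no stratum, subgroup or interaction for chest pain, no score cut-off and no benchmark value. Chest pain has its own entry at admission in the Schedule of Events (2.3) and in 2.3.2.1.

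**The concern.** Two things differ at once between this study and the one that produced 0.880 and 0.680: the patient cohort and the mix of presenting complaints. Vital signs, heart rate variability and type of event may all differ between a breathless patient and one with chest pain, so the score's accuracy may differ too. If the pooled accuracy departs from the published figures, the sponsor cannot say whether the algorithm travels poorly to a new cohort or was applied to a different case mix. If it agrees, weak performance in one group may be masked by the other.

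A second gap compounds this. Section 1.1 promises sensitivity and specificity, but Section 3.2 delivers the AUC of a fitted model. That says nothing about how the existing score performs at 4 or higher.

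**Working it through.** **1. The plan's own figure.** Section 3.7 gives 634 analysed subjects. The Hsieh (1989) formula is n = (z_a + z_b·exp(−β²/4))² × (1 + 2pδ)/(pβ²), with δ = [1 + (1 + β²)exp(5β²/4)]/[1 + exp(−β²/4)]. With β = 0.747, p = 0.05, two-sided α = 0.05 and 80% power, n = 317.1. Dividing by (1 − 0.5) gives 634.2, so 634 reproduces if 0.500 is entered as the squared multiple correlation. This sizes a test that one coefficient is non-zero. It does not size an estimate of sensitivity or a comparison with published values.

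**2. Event rate implied by the published figures.** From the PPV: 0.195 × 0.32 / (0.88 × 0.805 + 0.195 × 0.32) = 0.0624/0.7708 = 8.1%. From the NPV: 0.68 × 0.015 / (0.68 × 0.015 + 0.985 × 0.12) = 0.0102/0.1284 = 7.9%. The four figures agree with one another. Section 3.7 uses 5% at the mean of the covariate, which is a different quantity, so both 5% and 8.1% are carried forward.

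**3. What case mix alone can do.** The documents give neither the chest-pain share nor the accuracy in other complaints, so these inputs are assumptions. Let c be the chest-pain share: of event-free subjects for specificity, of events for sensitivity. Pooled value = c × (chest-pain value) + (1 − c) × (value elsewhere).

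| Measure | Chest pain | Elsewhere (assumed) | c = 0.7 | c = 0.5 | c = 0.3 |
|---|---|---|---|---|---|
| Specificity | 0.68 | 0.50 | 0.63 | 0.59 | 0.55 |
| Specificity | 0.68 | 0.80 | 0.72 | 0.74 | 0.76 |
| Sensitivity | 0.88 | 0.70 | 0.83 | 0.79 | 0.75 |

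In every row the algorithm performs exactly as published in chest pain, yet the pooled value moves. For specificity the shift would be visible. With 634 − 32 = 602 event-free subjects, a pooled 0.626 has a half-width of 1.96 × √(0.626 × 0.374/602) = 0.039, so its upper limit of 0.665 lies below 0.68. For sensitivity, values of 0.75 to 0.83 lie inside the all-subject interval around 28/32 (table below), so the data could not clearly show the shift.

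**4. What the stratum can deliver.** Exact (Clopper-Pearson) 95% limits for x out of n are the 0.025 quantile of Beta(x, n − x + 1) and the 0.975 quantile of Beta(x + 1, n − x). Observed accuracy is taken near 0.88 and 0.68, and the chest-pain share is assumed.

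| Event rate | Share | Subjects | Events | Detected | Sensitivity interval | Specificity interval |
|---|---|---|---|---|---|---|
| 5% | 100% | 634 | 32 | 28 | 0.710–0.965 | 0.640–0.717 |
| 5% | 70% | 444 | 22 | 19 | 0.651–0.971 | 0.633–0.724 |
| 5% | 50% | 317 | 16 | 14 | 0.617–0.984 | 0.625–0.733 |
| 5% | 30% | 190 | 10 | 9 | 0.555–0.997 | 0.604–0.745 |
| 8.1% | 70% | 444 | 36 | 32 | 0.739–0.969 | 0.631–0.724 |
| 8.1% | 50% | 317 | 26 | 23 | 0.698–0.976 | 0.623–0.734 |
| 8.1% | 30% | 190 | 15 | 13 | 0.595–0.983 | 0.605–0.748 |

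**5. How close the endpoints are.** The primary list (2.1.5.1 and 3.2) largely follows the composite that Section 1.1 reports for the chest-pain study, over the same 72 hours. It differs in that death is not a separate item (sudden unexpected death enters only through the cardiac-arrest definition in 2.1.6.2), VT must be sustained, and PCI or CABG counts without the recurrent-ischemia qualifier.

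**The case against.** The strongest reply is that the chest-pain figures were never declared the target. The study title, purpose and primary objective all concern ED patients with cardiopulmonary events in general. Section 1.1 asks for verification of results from more than one study, and the cardiac-arrest result is not tied to chest pain; the title of reference 3 describes critically ill ED patients. If the broad group is the intended population, the pooled result is the right estimate for it. This stands. A reader might infer that 0.880 and 0.680 are the sole standard, or that subjects without chest pain are a new indication; the documents support neither.

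Pooling is also not the main reason that success or failure cannot be read from the plan. No benchmark is set for any group and the cut-off is not applied, so splitting by complaint alone would not cure this. That stands too.

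Eligibility is not open-ended: the investigator's added symptoms must be judged cardiac or cardiopulmonary-related, within two triage tiers. And a chest-pain comparison would not be strictly like for like, because the composites differ.

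What the reply does not answer is attribution. The chest-pain study supplies the only numerical comparator and the closest composite. Anyone who sets the pooled result beside it will be unable to separate cohort from complaint. The explanatory variables are unnamed, so chest pain may or may not be among them, but a main effect would not give accuracy by complaint.

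**Conclusion.** The point holds as a cheap improvement. The plan cannot attribute a departure from the published accuracy to the new cohort rather than to case mix, and it does not evaluate the published cut-off at all. Under the assumed inputs, case mix alone could move pooled specificity from 0.68 to anywhere between 0.55 and 0.76, and pooled sensitivity from 0.88 to between 0.75 and 0.83. These figures illustrate the mechanism and are not predictions.

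A reader might go further and conclude that the verification should succeed or fail on the chest-pain patients alone. The documents do not support that. They name no such target, and the stratum would hold only about 10 to 22 events at a 5% rate (assumed share 30% to 70%), which is too few for sensitivity to carry the conclusion. Specificity is reasonably precise, about 0.60 to 0.75 even at a 30% share.

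**What to change.** In Section 3.2, pre-specify the sensitivity and specificity of the algorithm score at 4 or higher, with exact 95% confidence intervals, for three groups: all subjects, subjects with chest pain recorded at admission, and subjects without it.

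- Keep the all-subject result as the estimate for the enrolled population.
- Set the chest-pain result beside the published values as the closest comparison, and state how the composites differ (step 5 of the working).
- Do not make a claim of verification depend on the chest-pain stratum alone.

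The cost is a paragraph of SAP wording and one stratified table. Eligibility and data collection are unchanged, since chest pain is already recorded; the analysis assumes that the score is computed for each subject, as any verification requires. The drawback is imprecise sensitivity within strata, which should be acknowledged in the plan. Specifying the split now is more credible than choosing it after the data are seen.

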## 2.2.3 Exclusion Criteria

Candidates will be excluded from the study if any of the following conditions are present:

1. Pregnant or suspected pregnancy;
2. Significant trauma
3. Do Not Resuscitate order
4. Known as ward of the state

## 2.3 Study Procedures

Schedule of Events			
Hospital Stay Status	Admit	During	Discharge/ Withdrawal
Inclusion/Exclusion Criteria	X		
Informed Consent	X 		
Study Evaluations			
Demographics (date of birth/age, gender and ethnicity)	X		
Smoking status	X		
ED diagnosis (primary)	X		
Final diagnosis (primary)			X
Medications including beta-blockers, combined alpha and beta-blockers, digitalis, calcium channel blocker, bronchodilators, amiodarone, other anti-arrhythmics	X	X	X

Medical history, specifically a history of ischemic heart disease, diabetes, hypertension, dyslipidemia, stroke, cancer, respiratory disease, renal disease, congestive heart disease, PCI, CABG, MI)	X		
Physical exam [REDACTED]	X		
Glasgow Coma Score (GCS)	X		
Blood labs; specifically troponin and/or CKMB if available	X		
12-lead ECG (if patient is reporting chest pain)	X 		
Continuous 3-lead ECG recording of at least five minutes	X		
Chest Pain	X		
Symptom onset/peak within 24 hours of presentation	X		
Pain score	X		
MEWS Score	X		
Cardiopulmonary events (acute pulmonary edema, lethal arrhythmias, cardiogenic shock, myocardial infarction, percutaneous coronary intervention, coronary artery bypass surgery, recurrent ischemia requiring revascularization)	X	X	X
In-hospital cardiac arrest		X	
In-hospital death		X	
Status changes (admitted to ICU, admitted to ward, etc.)		X	
Length of stay			X
Adverse Events	X	X	X

1 Every effort will be made to ensure that consent is received from the patient or patient's legally authorized representative (LAR) within 24 hours of patient enrollment. If the patient or LAR refuses consent the patient will be withdrawn from the study.

[figure not shown]
2 If applicable

3 Serious adverse events must be reported to the Sponsor within 24 hours of becoming aware of the event, but no later than 10 days after the event.

### 2.3.1 Subject Enrollment

Subjects are enrolled in this study when they have:

- Met all eligibility criteria.

### 2.3.2 Evaluation Requirements

#### 2.3.2.1 Assessments

The following data points will be recorded:

- Inclusion/Exclusion Criteria
- Demographics (date of birth/age, gender and ethnicity)
- Smoking status
- ED diagnosis (primary)
- Final diagnosis (primary)
- Medications including beta-blockers, combined alpha and beta-blockers, digitalis, calcium channel blocker, bronchodilators, amiodarone, other anti-arrhythmics

- Medical history, specifically a history of ischemic heart disease, diabetes, hypertension, dyslipidemia, stroke, cancer, respiratory disease, renal disease, congestive heart disease, PCI, CABG, MI)
- Physical exam [REDACTED]  
[REDACTED]  
[REDACTED]
- 12-lead ECG (if patient is reporting chest pain)
- Continuous 3-lead ECG recording of *at least* five minutes within 30 minutes of ED triage
- Chest Pain
- Symptom onset/peak within 24 hours of presentation
- Pain score
- MEWS Score
- Cardiopulmonary events (acute pulmonary edema, lethal arrhythmias, cardiogenic shock, myocardial infarction, percutaneous coronary intervention, coronary artery bypass surgery, recurrent ischemia requiring revascularization)
- In-hospital cardiac arrest
- In-hospital death
- Status changes (admitted to ICU, admitted to ward, etc.)
- Length of stay

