### **2.1.5 Primary Outcome Measure**

#### **2.1.5.1 Cardiopulmonary events**

Cardiopulmonary events will be measured as the occurrence of any cardiopulmonary event, not limited to:

Cardiac arrest

Sustained ventricular tachycardia (VT)

Hypotension requiring inotropes or intra-aortic balloon pump (IABP) insertion

Intubation or mechanical ventilation

Complete heart block

Bradycardia requiring insertion of a pacing wire or external pacing, and

Percutaneous coronary intervention (PCI) or coronary artery bypass surgery (CABG),

\*all within 72 hours of presentation to the ED

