### **2.3.3.4 *Adverse Event CRF***

All adverse events and complications will be recorded and reported on the Adverse Event CRF. Serious adverse events must be reported to the Sponsor within 24 hours, but no later than 10 days after made aware of the event.

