## **3.2 Primary Outcome Measure**

The primary outcome measure is the occurrence of cardiopulmonary events. It will be measured as the occurrence of any cardiopulmonary event, within 72 hours of presentation to the ED, including:

Cardiac arrest

Sustained ventricular tachycardia (VT)

Hypotension requiring inotropes or intraaortic balloon pump (IABP) insertion

Intubation or mechanical ventilation

Complete heart block

Bradycardia requiring insertion of a pacing wire or external pacing, and

Percutaneous coronary intervention (PCI) or coronary artery bypass surgery (CABG).

For the primary outcome measure of occurrence of cardiopulmonary events, binary logistic regression will be used to estimate the probability that a cardiopulmonary

event has occurred given the values of explanatory variables, given by the following equation:

- $Y$  is the primary outcome measure  
 $Y_i = 1$  if a cardiopulmonary event has occurred  
 $Y_i = 0$  if there is no cardiopulmonary event
- $\pi_i$  = the probability of a cardiopulmonary event
- $X = (X_1, X_2, \dots, X_k)$  being the set of explanatory variables

*Model:*

$$\text{logit}(\pi_i) = \beta_0 + \beta_1 x_{i1} + \dots + \beta_k x_{ik}$$

A Receiver Operating Characteristic Curve will be constructed and the area under the curve will be calculated to assess the model sensitivity.

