### 3.3 Secondary Outcome Measure

The secondary outcome measure of the frequency of any cardiac event will be measured as the occurrence of any cardiac and cardiac-related events, not limited to:

1. In-hospital Death
2. In-hospital Cardiac Arrest
3. Composite cardiovascular outcome or intervention (Lethal Arrhythmias , Acute Pulmonary Edema, Cardiogenic Shock, Myocardial Infarction, Percutaneous Coronary Intervention, Coronary artery Bypass Surgery , New or Recurrent MI, Recurrent Ischemia requiring Revascularization)

For the secondary outcome measure of frequency of any cardiopulmonary event, multiple linear regression will be used to estimate the probability that an increase in the number of cardiopulmonary events given the values of explanatory variables, given by the following equation:

- $Y_i$  is the number of cardiopulmonary events
- $\pi_i$  = the probability of a cardiopulmonary event
- $X = (X_1, X_2, \dots, X_i)$  be the set of explanatory variables
- $p$ =number of  $\beta$  coefficients in the model (including the intercept)

*Model:*

$$y_i = \beta_0 + \beta_1 x_{i1} + \beta_2 x_{i2} + \dots + \beta_{p-1} x_{ip} + \epsilon_i$$

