### **3.6 Missing Data**

The primary analysis will be based on the data as observed. Two additional sensitivity analyses will be performed where subjects with missing data are (1) assumed to have no cardiopulmonary events and (2) assumed to have a cardiopulmonary event.

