#### **4.3 Case Report Form Review**

A database that is compliant with 21 CFR Part 11 will be used. eCRFs received from the site will be documented with their date of receipt and entered into the study database. If there is missing, incomplete, unclear or discrepant information recorded on eCRFs, a Data Clarification Form (DCF) will be generated. The DCF will be sent to the Investigator for completion and signed by the appropriate site personnel. The DCF will then be sent back to the Sponsor to update the database. All common modules are demographics, screening, adverse events, labs, medical history, medications, procedures, treatment discontinuation, study completion, and signatures.

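### The events listed for recording are those of the secondary composite; three of the seven primary components are not named and two have only a proxy

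*Combined protocol and SAP*

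**What the plan says.** Sections 2.1.5.1 and 3.2 make the primary outcome the occurrence of any of seven components within 72 hours of presentation. Among them are "Intubation or mechanical ventilation", "Hypotension requiring inotropes or intraaortic balloon pump (IABP) insertion" and "Bradycardia requiring insertion of a pacing wire or external pacing, and". The others are cardiac arrest, sustained VT, complete heart block, and PCI or CABG.

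Section 2.3.2.1, which sets out the data to be recorded, describes the event data point as "Cardiopulmonary events (acute pulmonary edema, lethal arrhythmias, cardiogenic shock, myocardial infarction, percutaneous coronary intervention, coronary artery bypass surgery, recurrent ischemia requiring revascularization". The Schedule of Events in Section 2.3 has the same line. Cardiac arrest and death in hospital have rows of their own.

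The items on that line match the secondary outcome in Sections 2.1.6.1 and 3.3, which begins "Composite cardiovascular outcome or intervention (Lethal Arrhythmias , Acute Pulmonary Edema, Cardiogenic Shock, Myocardial Infarction".

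Two more general sources are mentioned. Section 2.3.3.4 says "All adverse events and complications will be recorded and reported on the Adverse Event CRF". Section 4.3 lists the database modules: "All common modules are demographics, screening, adverse events, labs, medical history, medications, procedures, treatment discontinuation, study completion, and signatures". On missing data, Section 3.6 says "The primary analysis will be based on the data as observed". It adds two sensitivity analyses in which subjects with missing data are all counted as event-free, or all as having an event.

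**The concern.** The same term, cardiopulmonary events, has one meaning in the endpoint definition and another in the collection plan. The primary logistic regression and the ROC curve both rest on a binary Y built from the first meaning, while the sites are told to record the second.

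A site that follows the listed data points is not asked about three of the seven primary components. A patient who was intubated and had no other event could be coded Y = 0. Nothing on that record would be blank, so neither sensitivity analysis in Section 3.6 would touch it. If some sites pick such events up through adverse event or procedure entries and others do not, ascertainment of the primary outcome will differ among the 3 sites.

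The direction of the net effect on the event count is not known. Section 2.1.5.1 leaves its list open-ended, so secondary items that are collected, such as acute pulmonary edema or MI, might also be counted as primary events.

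**Working it through.** **Item match.** Each primary component (Sections 2.1.5.1 and 3.2) was looked for in the Schedule of Events and in Section 2.3.2.1.

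| Primary component | Where it could be found in the recorded data points | Status |
|---|---|---|
| Cardiac arrest | Own row | Named |
| PCI or CABG | On the event line | Named |
| Sustained VT | Lethal arrhythmias, a term the plan does not define | Proxy only |
| Hypotension needing inotropes or balloon pump | Cardiogenic shock, which is not equivalent; inotropes are not among the named medication classes | Proxy only |
| Intubation or ventilation | None | Not named |
| Complete heart block | None | Not named |
| Bradycardia needing pacing | None | Not named |

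Total: 2 named + 2 proxy only + 3 not named = 7.

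**Reverse match.** The recorded event line has seven items: acute pulmonary edema, lethal arrhythmias, cardiogenic shock, MI, PCI, CABG, and recurrent ischemia with revascularization. All 7 are in the secondary composite of Section 3.3. Only 2 of the 7 (PCI, CABG) are in the primary list.

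**Other possible sources.** The required ECG is one recording of at least five minutes, made within 30 minutes of triage, so it does not cover 72 hours. The redacted text belongs to the physical exam item, which is scheduled at admission only and is unlikely to hold later events. Section 2.3.3 describes four forms (eligibility, deviation, discontinuation, adverse event), and none is an event or endpoint form. No section links the adverse event or procedures records to the primary endpoint.

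**Scale.** The documents give no component rates, so the number of lost events cannot be computed. Section 3.7 gives a base: N = 634, β = 0.747, event proportion 0.050 at the mean of x, multiple correlation 0.500, two-sided α = 0.05, power 80%.

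The plan's figure reproduces with the Hsieh (1989) formula if 0.500 is entered as the squared correlation:

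- n = [z(0.975) + z(0.80)·exp(−β²/4)]² × (1 + 2Pd) / (Pβ²) ÷ (1 − R²), with d = [1 + (1 + β²)·exp(5β²/4)] / [1 + exp(−β²/4)]
- β² = 0.558, exp(−β²/4) = 0.870, d = 2.209
- (1.960 + 0.842 × 0.870)² = 7.247, and 1 + 2 × 0.05 × 2.209 = 1.221
- 7.247 × 1.221 / 0.0279 = 317.1, and 317.1 / 0.5 = 634.2, against 634 stated

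Expected events, taking x as standard normal (an assumption):

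- logit(0.050) = −2.944
- mean of expit(−2.944 + 0.747x) over x ~ N(0,1) = 0.0625
- 0.0625 × 634 ≈ 39.6 events, so one miscoded patient is 1/39.6 = 2.5% of all events
- with the plain 0.050: 0.050 × 634 = 31.7 events, and one patient is 3.2%

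As an illustration only, suppose missed events lower the proportion 0.050 by the same fraction and nothing else changes. Under the formula above, losing 10%, 30% or 50% of events takes power at 634 from 80% to about 76%, 66% or 52%. These fractions are assumptions, not estimates.

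**The case against.** The strongest reply is that the lists in the protocol are a summary and the eCRF is the actual instrument. Section 2.3.2.1 is plainly not exhaustive, since it leaves out adverse events, which the Schedule of Events includes. The forms described in Section 2.3.3 and the modules in Section 4.3 also name nothing for MEWS or the ECG, which are certainly collected, so the absence of an endpoint form from those lists is weak evidence. Adverse events are scheduled at admission, during the stay and at discharge. New ventilation or pacing could well meet the definition of a serious event in Section 2.4, and a procedures module could hold intubation or a pacing wire. A site might also file complete heart block under lethal arrhythmias, which would make the split 2 named, 3 proxy and 2 unnamed.

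Part of this stands. The eCRF may hold the missing fields, some events would probably be caught by these routes, and actual loss of events is not shown. What does not fall is the contradiction in the text. No section says that the primary components are taken from the adverse event or procedures records, so capture by that route would be incidental and could vary by site. Filing heart block under an undefined term is another example of non-uniform capture. The open-ended wording of Section 2.1.5.1 widens what may count as an event but creates no data field.

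**Conclusion.** The concern holds, and the plan is wrong as written. The endpoint definition and the collection plan contradict each other: of seven primary components, two are named among the recorded data points, two have only a proxy and three are absent. Recording the data exactly as listed can turn true primary events into Y = 0, and Section 3.6 has no means of showing it.

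Confidence is high for the mismatch, which rests only on comparing the lists. The size of any event loss is unknown. The figure of about 2.5% of events per miscoded patient is a scale, not an estimate, and depends on the Section 3.7 inputs and a standard normal x. This must be fixed because it concerns the primary outcome, the planned sensitivity analyses would not detect it, and the correction is cheap.

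**What to change.** In the Schedule of Events, Section 2.3.2.1 and the eCRF, list each primary component from Section 3.2 as its own yes/no item with onset date and time, so that the 72-hour window can be applied. Keep the secondary composite items on a separate line under a different label. State which form feeds the primary endpoint, and whether adverse event or procedures records may contribute to it.

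The cost is about five further items (sustained VT; hypotension needing inotropes or balloon pump; intubation or ventilation; complete heart block; bradycardia needing pacing) plus onset times. All come from the same hospital record, with no new procedure for the patient. If the eCRF already holds these fields, only the protocol text needs to change.
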